# 4.3. Number of Participants

200 Asthmatic male and female participants, as well as 30 healthy volunteers aged 18-85 will be used for this study.

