Xe dissolved phase MRI data will be reconstructed using a re-gridding method. The following ratios will be determined by the area-under-the curve obtained from spectroscopy: red-blood-cell to alveolar membrane ratio (RBC:membrane); RBC to gas ratio (RBC:gas); and the membrane to gas ratio (membrane:gas). Spectroscopic signals will be used to reconstruct perfusion and alveolar membrane maps.

Seven-day, 14-day and 1-year reproducibility of Xe MRI measurements will be determined using the coefficient of variation and intraclass correlation coefficients (ICC). The changes in regional VDP will be evaluated for all participants after 2 years pre- and post-salbutamol.

We will evaluate Pearson correlations for MRI measurements (VDP, TCV) with CT (WA%), spirometry and plethysmography measurements to determine whether structure relates to function (and *vice versa*). We will also evaluate the relationship between sputum, biopsy, CT and MRI measurements. Significant differences in Pearson correlations will be determined using 95% Confidence Intervals (CI). To evaluate agreement between measurements, Bland-Altman plots will be generated to show the differences between WA% and He VDP with Xe VDP.

Univariate and multivariate regression models will also be used and adjusted for confounders to assess correlations of imaging measurements with dyspnea score, and asthma control measures for a better understanding of the relationship between imaging and established/validated clinical measurements of asthma. We will also examine the relationship between clinically defined asthma severity and imaging. In each of these models, we will employ a forward stepwise selection modeling process to maximize the

DATE: November 15, 2024

efficiency, while maintaining the validity of the modeling process. We will select only those covariates with a p-value of 0.25 or less and include only those variables that have a p-value of 0.2 or less in the final model. From these models, we will determine the total  $R^2$  values as well as partial  $R^2$ . The Holm-Bonferroni correction will adjust for multiple comparisons.

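### Regressions meant to adjust for confounders keep covariates only by forward p-value rules (0.25, then 0.2), which can drop real confounders, overstate R² and make p-values too small

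*Protocol*

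**What the plan says.** All of this stands in Section 8 of the protocol (Image Analysis and Statistical Analysis Plan).

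- Purpose: "Univariate and multivariate regression models will also be used and adjusted for confounders to assess correlations of imaging measurements with dyspnea score". Asthma control is a further outcome, and models relating clinically defined severity to imaging follow.
- Method: "In each of these models, we will employ a forward stepwise selection modeling process to maximize the" efficiency of the modelling. The same sentence says that validity is maintained.
- Thresholds: "We will select only those covariates with a p-value of 0.25 or less and include only those variables that have a p-value of 0.2". Both limits are inclusive, and the second governs what stays at the end.
- Reporting: "From these models, we will determine the total" R², and partial R² as well.
- Multiplicity: "The Holm-Bonferroni correction will adjust for multiple comparisons". No family of tests is named.

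No confounder is named or exempted from the thresholds, the number of candidate covariates is not given, and no shrinkage or validation of R² is stated. Section 4.3 gives the size: "200 Asthmatic male and female participants, as well as 30 healthy volunteers aged 18-85 will be used for this study".

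**The concern.** Two stated rules conflict. A confounder belongs in the model because it relates to both the imaging measure and the outcome, whatever its p-value in this sample. Section 8 keeps it only if that p-value is 0.2 or less. A confounder that is highly correlated with the imaging measure has a large standard error, so it is the one most easily removed. Its removal also does most harm, because its effect then passes to the imaging coefficient.

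The second problem is that R² and p-values are read from a model chosen on the same data, as if it had been fixed beforehand. Selection keeps the terms that happened to fit well, so R² is too high and p-values are too small.

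The first hypothesis in Section 3 predicts that MRI abnormalities correlate both significantly and strongly with dyspnea, quality of life and control. Significance and strength are the two quantities that this procedure distorts. These models are among the analyses that address that hypothesis.

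**Working it through.** The protocol gives no R², power or error-rate figure for these models, so there is none to reproduce. The check is of how the rule behaves. From the protocol: thresholds 0.25 and 0.2; n=200 asthma participants (Section 4.3); n=60 for the first participants with extra visits (Section 4.1). Assumed: two-sided 0.05, since no alpha is stated for the regressions; one confounder, with the ranges below; 10 or 20 candidates.

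The text allows two readings: either the imaging term is held in and only the adjusters are selected, or all measures compete as candidates. Both were checked.

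**Reading A: imaging term held in, one confounder subject to the rule.** Outcome = g × confounder + noise (SD 1). The imaging term has correlation ρ with the confounder and no effect of its own. With both terms in the model, the confounder's test statistic has mean of about g√(n(1−ρ²)). The confounder is dropped when the statistic lies within ±1.28 (p > 0.2):

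P(drop) ≈ Φ(1.28 − m) − Φ(−1.28 − m), with m = g√(n(1−ρ²)).

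- n=200, g=0.15, ρ=0.7: m = 0.15 × √102 = 1.51; P ≈ 0.408 − 0.003 = 0.41.
- n=200, g=0.3, ρ=0.3: m = 0.3 × √182 = 4.05; P ≈ 0.003.
- n=60, g=0.15, ρ=0.7: m = 0.15 × √30.6 = 0.83; P ≈ 0.674 − 0.017 = 0.66.
- n=60, g=0.3, ρ=0.3: m = 0.3 × √54.6 = 2.22; P ≈ 0.17.

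Once the confounder is out, the imaging slope has mean ρg. For ρ=0.7 and g=0.15 that is 0.105, although the true slope is 0.

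Simulation (1,500 runs per row):

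| n | ρ | g | Confounder dropped | Type I error, selected | Type I error, forced in |
|---|---|---|---|---|---|
| 200 | 0.5 | 0.15 | 32.0% | 0.085 | 0.051 |
| 200 | 0.5 | 0.3 | 0.7% | 0.053 | 0.049 |
| 200 | 0.7 | 0.2 | 25.1% | 0.159 | 0.062 |
| 60 | 0.5 | 0.15 | 65.3% | 0.069 | 0.045 |
| 60 | 0.5 | 0.3 | 26.0% | 0.078 | 0.048 |
| 60 | 0.7 | 0.2 | 63.3% | 0.122 | 0.055 |

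Over the wider grid (g 0.15 to 0.3, ρ 0.3 to 0.7), the confounder is dropped in about 0.3 to 42% of runs at n=200 and 20 to 67% at n=60. Type I error is about 0.05 to 0.16.

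**Reading B: all measures are candidates, none has any effect (true R² = 0).** There were 600 runs per setting with independent candidates. Ranges cover a univariate screen at 0.25 before selection, and no screen.

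| n | Candidates | Kept | Mean R² | Kept terms with p<0.05 | Any rejection, Holm over kept terms only | Any rejection, Holm over all terms, fixed model |
|---|---|---|---|---|---|---|
| 200 | 10 | 1.9–2.0 | 0.031–0.033 | 28% | 0.225–0.237 | 0.047–0.053 |
| 200 | 20 | 3.6–3.9 | 0.060–0.063 | 29% | 0.252–0.267 | 0.050 |
| 60 | 10 | 1.9–2.1 | 0.105–0.111 | 30–32% | 0.258–0.280 | 0.047–0.058 |
| 60 | 20 | 3.2–4.3 | 0.183–0.222 | 39–40% | 0.333–0.415 | 0.042–0.045 |

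Repeat runs with 20 candidates gave R² of about 0.07 at n=200 and up to 0.25 at n=60. For comparison, a fixed model with 1.9 noise terms has expected R² of 1.9/199 = 0.010 at n=200 and 1.9/59 = 0.032 at n=60. Adjusted R² does not remove the bias: it averaged 0.02 to 0.16 across the settings.

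A simple check on the p-values: a null term kept at p ≤ 0.2 has p < 0.05 with probability 0.05/0.2 = 0.25, not 0.05.

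**The case against.** The synopsis labels the study exploratory, no treatment decision hangs on these models, and Section 8 presents them as a way to understand relationships. The thresholds are lenient, so fewer confounders are lost than at 0.05. With the imaging term held in, 5 or 8 null adjusters and n=200, type I error for the imaging term is 0.052 to 0.055. A confounder of effect 0.3 with correlation 0.3 is lost in under 0.5% of runs. All of this stands, and it limits the size of the problem. It does not remove the conflict between adjusting for confounders and deleting them by p-value, and the harder cases remain.

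Some stronger readings are not supported:

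- A reader might infer that Holm is applied to the surviving terms only. Section 8 names no family, and a separate SAP may define one. The error of 0.22 to 0.42 is therefore conditional on that reading.
- A reader might take 20 candidates as the plan's number. Section 8 lists about 18 imaging measures (whole-lung, centre-slice and six regional ADC values, two ADC gradients, five volume measures, three dissolved-phase ratios), so 20 is plausible. It does not say that they enter these models.
- A reader might take the n=60 figures as typical. The regressions are not restricted to that subset, and baseline models can use up to 200 participants.
- A reader might say that selection inflates p-values. It makes them too small; what rises is R² and the false-positive rate.

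**Conclusion.** The point holds. Section 8 fixes a selection rule that works against the stated purpose of the models, and its assurance that validity is maintained is not correct. Under favourable inputs (n=200, a strong confounder, low correlation with imaging) the harm is negligible. Under less favourable but plausible ones, type I error for the imaging term roughly triples, to about 0.16. If many measures compete, apparent R² with no true association is about 0.03 to 0.07 at n=200, and about 0.18 to 0.25 at n=60 with 20 candidates.

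These sizes rest on assumed confounder effects, correlations and candidate counts, on independent noise candidates in Reading B, and on two-sided 0.05. The direction of each distortion does not depend on those choices. The exploratory label lowers the consequence but does not make selected-model R² and p-values valid.

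**What to change.** 1. Delete the 0.25 and 0.2 thresholds for adjustment covariates. For each imaging measure and each outcome, fit a model with confounders named in advance on clinical grounds and forced in whatever their p-values.
2. Choose that list with care. FEV₁ should enter only where it is neither part of the outcome (it is item 7 of the ACQ in Appendix VII) nor on the pathway under study, since it may express the same obstruction as VDP. Smoking history can vary little among asthma participants, because Section 5.1 caps it.
3. State that Holm applies over all planned imaging-by-outcome tests.
4. Report partial R² from the fixed model and a bootstrap optimism-corrected total R². Repeat any selection inside each bootstrap sample.
5. Label any stepwise model that is kept as descriptive, without confirmatory p-values.

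The cost is a change of wording, a few degrees of freedom per model and a bootstrap. No new data are needed. R² and p-values will look less favourable.

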#### 2. OBJECTIVES OF STUDY

- Acquire Xe MRI and optimize analysis methods to generate *in vivo* measurements
- Evaluate Xe MRI measurements over time and in response to therapy, relate them to airflow, dyspnea, airway remodeling and inflammation and validate using x-ray computed tomography (CT) and histology
- Evaluate image analysis methods that generate Xe MRI temporal lung function maps as image guidance/therapy planning tools for targeted asthma therapy
- Develop Xe MRI structure-function models computationally to understand mechanisms of localized therapy response
- Evaluate oscillometry outcomes of the respiratory system as they correlate to lung function abnormalities detected using Xe MRI
- For the subset of patients identified as underperceivers using asthma control and quality of life questionnaires, we will acquire fMRI to determine if severe asthmatics with poor control exhibit baseline differences in brain structure and function compared to healthy volunteers, and if these alterations influence asthma symptom perception.
- To determine if differences in brain structure and function are related to lung function abnormalities quantified by pulmonary MRI
- In healthy volunteers and the subset of asthmatic participants identified as underperceivers, to determine if differences exist in resting state brain connectivity pre- and post-Methacholine challenge
- In the subset of asthmatic participants, to evaluate the differences in resting state brain connectivity compared to healthy volunteers post-Methacholine Challenge

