# 4.1.1. Methacholine Challenge

Methacholine Challenge will be performed for healthy volunteers and asthmatic participants in the Robarts Pulmonary Function Laboratory according to the American Thoracic Society Guidelines (ATS). After recording baseline FEV1, participants will inhale Methacholine solutions up to and including the concentration of Methacholine required to decrease FEV1 by 20% from baseline (PC20). After completion of dyspnea score and He or Xe at PC20, 400 μg of Salbutamol (4 puffs) will be administered followed by spirometry 20 minutes post-administration. Methacholine challenge will be performed at V1 baseline only.

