Logs and records of Xe and He gas exposure will be maintained for every participant in this study. Adverse experiences and pulse oximetry measurements during MRI will be recorded. If oxygen saturation falls to <80% continuously for ≥15 seconds, scanning will be discontinued, and the patient will be provided supplemental oxygen as necessary until oxygen saturation recovers to the patient's baseline value. This patient will then be discontinued from the study.

Participants undergoing resting state fMRI (healthy volunteers and the subset of asthmatic participants identified as underperceivers) will also be placed in the 3T MR scanner with a 32-channel brain coil fitted around their head. Hearing protection will be provided to each participant to muffle the noise produced by the gradient RF coils. A pulse

Protocol ROB0037, Robarts Research Institute Version 16

DATE: November 15, 2024

oximeter lead will be attached to all of the participants to monitor their heart rate and oxygen saturation. MRI will be performed for up to a period of 20 minutes. All participants will have supplemental oxygen provided via nasal cannula at a flow-rate of 2 liters per minute during the scanning process. Participants will undergo fMRI on two occasions during the first visit, each containing acquisition of an anatomical image, a BOLD signal image, and a diffusion tensor image. The sessions will be performed before and after the methacholine challenge for baseline and induced asthma attack or dyspnea conditions, respectively. Outlined in the table below are the appropriate pulse sequences designed for resting state fMR image acquisition:

Brain fMRI and lung MRI using Xe and/or He will be performed within five minutes of each other at both baseline and post-methacholine, and the order in which they are performed will be randomized for each participant and remain the same for both time points.

# Protocol ROB0037, Robarts Research Institute Version 16

DATE: November 15, 2024

MRI RSfMRI Protocol 1 - GE MR 750 Discovery (3T)													
Coil Selection: 32 Channel Head Coil  1. 3 Plane Localizer (2D FGRE)													
TR (ms)	TE (ms)	TI (ms)	FLIP ANGLE	FOV (cm)	FREQ MATRIX (mm)	PHASE MATRIX (mm)	SLICE THICKNESS (mm)	SLICE GAP (mm)	NEX	BANDWIDTH (kHz)	FREQ DIRECTION	ASSET	0:08
5	1.4	N/A	30	24	256	128	10	0	1	31.2	Unswap	N/A	
2. Calibr	ation Sca	ın (3D FS	PGR)										
													0:06
3. Sagitta	al T1 (3D	IR-FSPC	GR)										

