# 5. PARTICIPANT SELECTION CRITERIA

Male and females aged 18-85 will be used for this study. Participants will be recruited through the Asthma Centre located at St. Joseph's Hospital as well as the site's established database of Asthma patients. The London City-Wide Respirology practice serves over 1000 asthma patients annually.

30 healthy volunteers will also be recruited. Volunteers will include males and females aged 18-85. Healthy volunteers will be recruited via flyer advertisement in the community.

30 participants with asthma will be recruited from [name] practice and research program at the Firestone Institute, McMaster University, and will be included in our 200 asthmatic male and female participants.

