# 6. STUDY PROCEDURES

# 6.1. Screening Procedures for Study Entry

Eligibility for this study will be determined by the participant's clinical history, including respiratory disease and medication history. In addition, the investigator or designate shall discuss with each participant the nature of the study, its requirements and its restrictions, and an informed consent document will be signed. Each participant will be assigned a unique Study Number that will serve to identify participant study documentation. If a participant fails to qualify for enrollment, his/her Study Number may not be reused for another participant.

Participants performing fMRI will be either healthy volunteers or have been identified as having poor asthma control and demonstrate inaccurate perception of their asthma symptoms using asthma control and quality of life questionnaires. Specifically, these asthmatic participants are unable to sense sensations of dyspnea during asthma flair-ups. Participants who have suffered from a brain or head injury or participants that have diagnosed with an anxiety and depression disorder will be excluded from this part of the study.

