For participants undergoing fMRI, we will utilize an unpaired two tailed t-test to assess the differences of BOLD and DTI signal intensity between asthma underperceivers and healthy controls. Furthermore, we will assess Pearson correlations for fMRI measurements (BOLD signals and DTI data) with lung MRI and spirometry measurements. Spearman correlations will be used to analyze the relationship between fMRI measurements and Asthma Control Questionnaire (ACQ) scores. Significant differences in Pearson and Spearman correlations will be determined using 95% CI.

For healthy volunteers and asthmatic underperceivers undergoing fMRI, we will utilize a paired two tailed t-test to assess the within group differences of BOLD and DTI signal intensity before and after a methacholine challenge. Pearson correlations will be used to assess the relationship between quantitative fMRI data and spirometry measurements. Significant differences in Pearson correlations will be determined using 95% CI.

To demonstrate if differences exist in BOLD and DTI signal between asthmatics and healthy volunteers post methacholine challenge, we will utilize an unpaired two tailed t-test. Pearson correlations will be used to assess the relationship between quantitative fMRI data and spirometry measurements. Significant differences in Pearson correlations will be determined using 95% CI.

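### Both between-group fMRI comparisons are unadjusted t-tests between unmatched groups, so age or sex imbalance would bias them; separately, the contrast cannot by itself attribute a difference to underperception

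*Protocol*

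**What the plan says.** **Who is scanned.** Section 4.1.2 limits brain imaging to two groups: "Participants undergoing resting state fMRI (healthy volunteers and the subset of asthmatic participants identified as underperceivers". Section 6.1 adds that the asthma group is also selected for poor control: "Participants performing fMRI will be either healthy volunteers or have been identified as having poor asthma control".

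**Where they come from.** Under Section 5, asthma participants come from a hospital asthma clinic, the site's own database and a second institution's practice. For controls, "Healthy volunteers will be recruited via flyer advertisement in the community". Both groups may be of either sex and aged 18 to 85. No matching, quota or stratification is stated. There are 30 healthy volunteers; the number of underperceivers is not given.

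**How they are compared.** At baseline, Section 8 says "we will utilize an unpaired two tailed t-test to assess the differences of BOLD and DTI signal intensity between asthma underperceivers and healthy controls". After the challenge, the same kind of test is named: "To demonstrate if differences exist in BOLD and DTI signal between asthmatics and healthy volunteers post methacholine challenge, we will utilize an unpaired two tailed". Neither test has covariates. Within each group, pre- and post-challenge scans are compared by a paired t-test. fMRI measures are also correlated with lung MRI, spirometry and the Asthma Control Questionnaire (ACQ).

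**What is asked.** The relevant objective in Section 2 has two halves: whether poorly controlled asthmatics differ from healthy volunteers at baseline, and "if these alterations influence asthma symptom perception".

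**The concern.** Two separate problems sit in the same contrast.

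The first is ordinary confounding. The groups are drawn by different routes over a very wide age range, and the named tests allow for neither age nor sex. If the BOLD or DTI measures vary with age or sex, any imbalance passes straight into the estimated group difference.

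The second is attribution. Everyone with asthma who is scanned is also an underperceiver with poor control, and everyone else scanned is healthy. Asthma, its treatment, poor control and underperception therefore change together. A significant difference could be read as a brain signature of blunted perception when it might reflect any of the others.

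At stake are a false-positive rate above the nominal level in two of the sub-study's tests, and the interpretation of one objective.

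**Working it through.** The protocol gives no effect size, SD, power or underperceiver number for these tests, so there is no figure of its own to reproduce. Every numerical input below other than the 30 volunteers is an assumption.

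**1. Size of an age bias.** Inputs: 30 per group (30 volunteers from the protocol, 30 underperceivers assumed), age SD 15 years, gap in mean age *g*, within-group correlation *r* of the measure with age, no true group effect, two-sided 5% test.

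The spurious difference in SD units is d = (g / 15) × r. The noncentrality is d × √(30/2) = d × 3.873, with 58 degrees of freedom.

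| Age gap | r | d | Noncentrality | Rejection rate |
|---|---|---|---|---|
| 10 years | 0.2 | 0.13 | 0.52 | 8% |
| 10 years | 0.4 | 0.27 | 1.03 | 17% |
| 10 years | 0.6 | 0.40 | 1.55 | 33% |
| 15 years | 0.2 | 0.20 | 0.77 | 12% |
| 15 years | 0.4 | 0.40 | 1.55 | 33% |
| 15 years | 0.6 | 0.60 | 2.32 | 63% |

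A simulation of the planned t-test (20,000 runs per setting) with other assumed inputs points the same way. It used 30 volunteers against 15, 30 or 60 underperceivers, an age shift of 0.5 or 1 SD, and r of 0.3, 0.5 or 0.7. Rejection ran from 7.4% to 87.1%, against about 5% with balanced ages.

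**2. Does adjustment repair this?** Simulating a linear model with group and age (3,000 runs, 30 per group, r = 0.5, no group effect) gave rejection rates of 5.0% for a 1 SD age shift and 4.6% for a 0.5 SD shift. The nominal level is restored.

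**3. Does adjustment help attribution?** Take ages balanced, 30 per group, and a total group difference of 0.5 SD. The unadjusted t-test rejects in:

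- 48.6% of runs if the difference is due wholly to asthma;
- 47.5% if it is due wholly to perception;
- 47.3% if it is half each.

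These are equal within simulation error, as they must be, because the data contain only the sum of the two effects. With age adjustment and a pure asthma effect of 0.5 SD, the test still rejects in 57% to 58% of runs. Adjustment removes the age bias and leaves attribution where it was.

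**4. Which tests are affected.** The two unpaired tests are. In the paired pre/post tests each participant is their own control, so age or sex differences between groups do not bias them.

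**The case against.** **The hypotheses do not claim attribution.** Section 3 asks for a baseline difference from healthy volunteers, a correlation with lung MRI, a change after methacholine and a post-challenge difference. Each has an analysis in Section 8. Perception is the second half of one of four fMRI objectives in a study labelled exploratory. This stands. A reader might infer that the brain imaging as a whole cannot answer its question; the documents support that only for the perception clause.

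**Lack of matching is not why perception cannot be isolated.** This also stands. The cause is the missing group of asthma participants with accurate perception, so the two problems need separate remedies.

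**Section 8 already plans confounder-adjusted regressions of imaging measurements on dyspnea score and asthma control.** These do not cover the two group comparisons, which are specified separately as t-tests. The term used for imaging is broad enough that it might include fMRI, however. A reader might infer that no planned analysis links fMRI to dyspnea, and the text does not allow that to be said flatly.

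**A statistical analysis plan not shown could add covariates.** It could, but the protocol names the test, so this is a stated choice rather than an omission.

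**Nothing suggests a gap of 10 to 15 years.** This is correct. Both groups share the same permitted range, and the rejection rates show sensitivity, not an expected error rate.

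**The unequal post-challenge state.** The second scan represents one of the "baseline and induced asthma attack or dyspnea conditions, respectively", and volunteers without respiratory disease may respond less to methacholine. A reader might call this a flaw, but a different response to the challenge is close to what the hypothesis tests, and the documents do not quantify it.

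**Conclusion.** The point holds in two limited parts.

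- **Bias.** Both between-group fMRI tests are open to age and sex imbalance that the plan neither prevents by design nor removes in analysis. With 30 per group, an age SD of 15 years, a 10-year gap and an age correlation of 0.2 to 0.6, all assumed apart from the 30 volunteers, the nominal 5% test rejects in about 8% to 33% of studies with no true group effect. The actual size depends on an imbalance the documents do not report.
- **Interpretation.** The contrast can show that poorly controlled asthma underperceivers differ from healthy people. It cannot by itself show that the difference concerns perception, whatever covariates are added.

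The documents do not support extending this to the paired pre/post tests or to the other fMRI objectives as a group. For an exploratory sub-study this is a worthwhile correction at little cost, not a failure of the design.

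**What to change.** 1. In Section 8, replace the two unpaired t-tests with linear models of each BOLD or DTI measure on group, adjusted for age and sex. The cost is two degrees of freedom (58 falls to 56 at 30 per group) and a change of wording. No extra scans are needed.
2. State in Section 8 that a group difference shows that poorly controlled asthma underperceivers differ from healthy people and is not attributed to underperception. This costs nothing.
3. Optionally, add an exploratory correlation, within the asthma fMRI group, of fMRI measures with the dyspnea score taken at PC20. Section 4.1.1 already places that score before salbutamol ("After completion of dyspnea score and" the gas MRI). Acknowledge the restricted range, since these participants are selected for poor sensing of dyspnea. Use the score itself rather than its rise, because no separate pre-challenge score is clearly scheduled.

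Matching volunteers on age and sex would also help, but the study began in 2013 and the documents do not say whether any remain to be recruited, so the remedy should not depend on it.

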#### 3. HYPOTHESES

- Asthma lung functional abnormalities can be quantified using 129Xe MRI over 2 years correlate significantly and strongly with dyspnea, pulmonary function and sputum measurements as well as indices of asthma quality of life and control. In addition, MRI VDP measured annually over a decade reflects significantly worse remodeling or will improve in response to therapy in those participants who opt for an annual visit.
- Xe MRI ventilation abnormalities are related to airway morphologies due to bronchospasm, airway structural remodeling and inflammation and these can be validated using CT and histology measurements of endobronchial biopsy samples;
- 129Xe MRI temporal functional maps will show significant correlations with functional images acquired 1 year later.
- Asthma underperceivers with poor control will exhibit significant baseline differences in fMRI BOLD contrast and DTI signal data compared to healthy volunteers.

DATE: November 15, 2024

- Quantitative fMRI data will be significantly correlated to pulmonary MRI data that quantifies abnormalities in lung function.
- Healthy volunteers and asthma underperceivers will show significant differences in BOLD contrast after undertaking a Methacholine challenge
- BOLD contrast will be significantly different between asthmatics and healthy volunteers post Methacholine challenge

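### The post-methacholine fMRI comparison uses post-challenge values alone, so it cannot separate a different response to methacholine from a baseline difference that persists

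*Protocol*

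**What the plan says.** Protocol Section 4.1.2 (MRI) provides two brain scans per fMRI participant at the same visit: "Participants will undergo fMRI on two occasions during the first visit", and "The sessions will be performed before and after the methacholine challenge for baseline and induced asthma attack or dyspnea conditions, respectively".

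Section 3 (Hypotheses) makes two between-group predictions for the fMRI subset. Before the challenge: "Asthma underperceivers with poor control will exhibit significant baseline differences in fMRI BOLD contrast and DTI signal data compared to healthy volunteers". After it: "BOLD contrast will be significantly different between asthmatics and healthy volunteers post Methacholine challenge". The matching objective in Section 2 is "to evaluate the differences in resting state brain connectivity compared to healthy volunteers post-Methacholine Challenge".

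Section 8 then fixes three sets of t-tests:

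- an unpaired test of underperceivers against healthy controls, with no time point stated and read here as the baseline comparison;
- within each group, a "paired two tailed t-test to assess the within group differences of BOLD and DTI signal intensity before and after a methacholine challenge";
- for the post-challenge question, the test of whether "differences exist in BOLD and DTI signal between asthmatics and healthy volunteers post methacholine challenge, we will utilize an unpaired two tailed t-test".

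None of these carries a covariate. The regression models for lung imaging in the same section, by contrast, are adjusted for confounders. On recruitment, Section 5 says "Healthy volunteers will be recruited via flyer advertisement in the community", while asthmatic participants come from clinics and an existing patient database. Both groups span ages 18 to 85, and no matching is described.

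**The concern.** If the baseline hypothesis is true, the post-challenge hypothesis can be confirmed by the same difference carried forward, even when methacholine affects both groups identically. The plan then gains nothing from the challenge in its between-group comparison, although the pre-challenge scan needed to do better is taken at the same visit. The reverse can also occur: a real difference in response that runs against the baseline gap can cancel it and leave nothing visible after the challenge.

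Two related weaknesses affect the same tests. The groups are recruited through different channels and cover a wide age range, so an unadjusted difference may partly reflect age or sex. In addition, the objectives ask about resting-state connectivity, while the tests are specified on the signal intensity of BOLD and DTI.

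**Working it through.** The protocol gives no power calculation, effect size or SD for the fMRI subset, so there is no planned figure to reproduce.

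**What each test estimates.** Let the baseline means be μA (asthmatic) and μH (healthy), and the mean changes after methacholine δA and δH.

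- Baseline unpaired test: μA − μH
- Paired tests: δA and δH, each against zero
- Post-challenge unpaired test: (μA − μH) + (δA − δH)
- Differential response: δA − δH, which is not tested

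The post-challenge test sees only the sum of two terms, and Section 3 predicts that the first is not zero. The paired tests do not fill the gap, because significance in one group and not in the other is not a test of δA − δH. For example, suppose both groups truly change by the same 0.5 SD of the change score. Paired-test power is 0.754 with 30 participants and 0.438 with 15. The two tests then disagree in 2 × 0.754 × 0.246 = 37% of trials (30 and 30), or 0.754 × 0.562 + 0.246 × 0.438 = 53% (30 and 15).

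**Illustration of size.** Inputs: 30 healthy volunteers (Section 4.3). Assumed: 15, 30 or 60 underperceivers, since the subset size is not stated; alpha 0.05 two-sided, since only two-tailed is stated; SD 1 at both times; δA = δH; baseline gap d.

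The post-only test has noncentrality d / √(1/30 + 1/nA) on 28 + nA degrees of freedom. For nA = 30 and d = 0.5 this is 0.5 / 0.258 = 1.94 on 58 df, which gives 48%.

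| Underperceivers | d = 0.3 | d = 0.5 | d = 0.8 |
|---|---|---|---|
| 15 | 15% | 34% | 70% |
| 30 | 21% | 48% | 86% |
| 60 | 26% | 60% | 94% |

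In simulations with 30 per group, pre-post correlation ρ of 0.3 to 0.7 and d of 0.5 or 0.8, a between-group t-test on change rejects in about 5% of trials.

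**Why not ANCOVA on the pre-challenge value.** With a true baseline gap and no differential response, the ANCOVA group term has expectation d − ρd = d(1 − ρ), which is not zero. In the same simulations it rejects in 12% to 27% of trials at d = 0.5 and in 23% to 54% at d = 0.8.

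**Masking.** With a baseline gap of +0.5 and a differential change of −0.5, the post-challenge difference is 0.5 − 0.5 = 0. The post-only test rejects in 5% of trials. The change test rejects in 36%, 47% and 69% at ρ = 0.3, 0.5 and 0.7.

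**Price of using change.** The variance of change is 2(1 − ρ), which equals the single-scan variance at ρ = 0.5. Below that correlation the change test has less power than the post-only test. Above it the change test gains: with no baseline gap, a true differential effect of 0.5 SD and ρ = 0.7 (30 per group), power is 47% post-only and 69% for change.

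**Outcome.** The Section 2 objective names connectivity, and the Section 8 tests name signal intensity. The imaging table in Section 4.1.2 lists a 6-minute resting-state series with a repetition time of 2500 ms, about 360 / 2.5 = 144 volumes. A connectivity measure can therefore be derived from data already being acquired.

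**The case against.** The strongest reply is that the objective and the hypothesis ask only whether the groups differ after the challenge, and an unpaired test on post-challenge values answers that literally. This stands. It also means that the percentages in the table are power to detect a real post-challenge difference. They become error rates only if the question is differential response.

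A reader might infer that the plan will report a baseline difference as a methacholine effect. The protocol does not support that: nowhere does it attribute this comparison to methacholine. Nor does it say that the two within-group tests will be set against each other to infer a group difference. Nor is the pre-challenge scan unused across the plan, since it enters the paired tests and, as read here, the baseline comparison. If changes were reported with standard errors, a reader could combine them by hand.

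Some detail, such as the choice of brain regions or of DTI summary measures, may properly sit in a statistical analysis plan that is not shown. DTI is also described in the protocol as informing on connections, so the outcome point is a mismatch of wording to be resolved. It does not prove that connectivity will never be derived.

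What remains is that Section 8 itself fixes the tests, none of them compares change between groups, and none adjusts for age or sex.

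**Conclusion.** The point holds in this limited form. The post-challenge test describes a state. Given the predicted baseline difference, it cannot support any statement about response to methacholine, and the separate paired tests do not supply the missing contrast. The comparison is also unadjusted between groups recruited in different ways, and its stated outcome does not match the connectivity objective.

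The size cannot be fixed from the protocol. The 34% to 86% range for baseline gaps of 0.5 to 0.8 SD with 15 to 30 underperceivers is a set of scenarios resting on an assumed subset size, effect size and alpha; the comparisons with change and ANCOVA also assume the pre-post correlation. Severity is moderate: the study is labelled exploratory, fMRI concerns a subset, and fMRI is not among the efficacy parameters in the synopsis.

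**What to change.** - Keep the post-challenge between-group comparison, and state that it describes the post-challenge state and will not be attributed to methacholine.
- Add a between-group test of pre-to-post change, either as group-by-time in a mixed model or as a regression of change on group, with age and sex as covariates. Do not use ANCOVA on the pre-challenge value, because the groups are not randomised and are expected to differ at baseline.
- Adjust the baseline and post-challenge group comparisons for age and sex.
- Name as the tested outcome a connectivity measure derived from the BOLD series, so that Section 8 matches the objectives in Section 2.

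The cost is revised wording and slightly more analysis, with no added scan or participant. The downside is that the change test has less power than the post-only test if the pre-post correlation is below 0.5. Keeping both comparisons limits that loss.
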